## 1. SUMMARY OF TRIAL DESIGN

This is a prospective, open-label, single-center trial to compare the efficacy of two different standard care approaches for MRI-ultrasound fusion-targeted prostate biopsy in men with high-suspicion lesions demonstrated on multi-parametric magnetic resonance imaging (mpMRI).

Subjects are enrolled on the basis of elevated clinical suspicion for prostate cancer and area of high suspicion on mpMRI. Subject participation includes one standard care biopsy session during which both transperineal and transrectal biopsies will be obtained using ultrasound/MRI fusion guidance to sample suspicious lesions identified on MRI. A follow-up visit after one week will be in accordance with current post-biopsy management practices, and further clinical management will proceed as per standard of care following the biopsy results.

The purpose of this study is to determine whether image-guided transperineal prostate biopsy can better characterize suspicious lesions in the prostate than transrectal biopsy. Accurate characterization of possible cancer foci is dependent on adequate targeting of suspicious lesions. Thus, the primary endpoint of the trial will be to determine the comparative efficacy of both approaches to accurately sample target lesions, which will be inferred from measuring the core-cancer length (CCL) in each positive core. Larger CCL when targeting the same lesion corresponds to better target sampling and will allow comparison of the relative ability of each biopsy approach to characterize lesions within the prostate.

### 2.1 OBJECTIVES AND SCIENTIFIC AIMS

#### Primary Objective:

1. To assess the comparative efficacy of image-guided transperineal versus transrectal biopsy in characterizing prostate cancer.

#### Secondary Objectives:

1. To demonstrate the feasibility and investigate the cancer detection rate (CDR) of targeted transperineal biopsy, which has been shown to have a lower risk of infectious complications than transrectal prostate biopsy.

#### Additional Observations:

1. Occurrence of adverse events.
2. Time spent in performing each biopsy technique.
3. Correspondence of MRI suspicion score to presence of clinically significant cancer detected on biopsy

## 2.2 HYPOTHESIS

We will test the hypothesis that transperineal targeted biopsy will result in larger core-cancer length than transrectal biopsy when targeted to the same cancerous lesion in the prostate.

## 3. BACKGROUND and OVERVIEW OF THE STUDY

### 3.1 Background and rationale

Prostate cancer is the most common malignancy and the second most common cause of cancer death in men in the Western hemisphere. When suspicion for prostate cancer is sufficiently raised by a combination of increased prostate-specific antigen (PSA) level and abnormal digital rectal examination, definitive diagnosis is reliant on biopsy of the prostate gland. Today, expert recommendations from the American Urological Association (AUA) propose transrectal ultrasound (TRUS)-guided prostate biopsy involving 10-12 cores for diagnosis in men with adequate suspicion for prostate cancer. This recommendation is based on optimizing the balance between adequate detection of clinically significant disease while minimizing detection of clinically insignificant disease, which has the potential to lead to overtreatment and increased morbidity.

Transrectal access to the prostate is the most common approach for systematic biopsy. However, a concerning limitation of this approach is the rising rate of infectious complications, which is the leading cause of hospitalization after biopsy despite antimicrobial prophylaxis. Additionally, impeded access to the anterior and apical regions of the prostate from the rectum has lead to undersampling of this region and reported false-negative rates as high as 30%. Poor sampling of regions of the prostate which may harbor cancer foci leads to misdiagnosis or mischaracterization of disease.

Transperineal biopsy of the prostate does not perforate the rectal wall, and thereby minimizes the risk of Gram-negative infection and rectal bleeding associated with transrectal biopsy. Because transperineal biopsy requires incision of the skin, the procedure presents a risk of infection and is often performed using local or regional anesthesia. Despite this, a 2012 meta-analysis concluded that transperineal biopsies do not have added risk of complications in comparison to transrectal biopsy, including infection. Additionally, a transperineal approach allows better access to the anterior region of the prostate. For patients with previously negative biopsies who still have an elevated risk of prostate cancer based on rising PSA, there is evidence to suggest that transperineal biopsies may be of clinical value in detecting previously undiagnosed disease. Improved sampling of cancer foci within the prostate can lead to more accurate characterization of disease, which ultimately serves as a major determinant in clinical decision-making. Finally, transperineal prostate biopsy follows the same physical approach as most modalities of focal therapy. Identification of cancers using this approach can thus optimize planning for focal therapy application in eligible patients.

Recently, the emergence of targeted biopsy using multi-parametric magnetic resonance imaging (mpMRI) to identify foci of potentially malignant disease prior to biopsy has raised the potential for selective target sampling. By using a combination of MRI sequences to evaluate the prostate, including T2, diffusion weighted, and dynamic contrast-enhanced images, a 5-point Likert scale is used to grade lesions based on suspicion for prostate cancer. This technique has demonstrated superior diagnostic power for clinically significant prostate cancer, with sensitivity exceeding 80% for detecting 0.2 cm^3 of Gleason 4 + 3 or above and 0.5 cm^3 of  $\geq$  Gleason 3 + 4 in one study. As a result, transrectal biopsy using MRI-targeting has demonstrated improvement in selectively identifying clinically significant cancer and reduced overdiagnosis of low-risk disease.

However, the current practice of transrectal needle placement still carries the same risks of undersampling of the anterior prostate and infection. Because a transperineal approach to the prostate allows improved sampling of the anterior region, it is reasonable to expect that an MRI-targeted biopsy using a transperineal approach may facilitate more accurate characterization of prostate cancer while also inherently limiting the risk of infection associated with transrectal biopsy.

The purpose of this study is thus to examine whether a transperineal approach to prostate biopsy using MRI-targeting can provide improved characterization of prostate cancer compared to a transrectal approach.

### **3.2 MRI-US Fusion Biopsy (Artemis)**

Computerized targeting of MP MRI lesions in our institution is routinely performed using Artemis™ software system. The Artemis-Profuse software requires an initial transrectal ultrasound measurement of the prostate in order to obtain a 3D image of the prostate on ultrasound. The computerized co-registration is then performed by software within the Artemis™ system and will fuse the MR imaging with real-time ultrasound imaging (this will require approximately 10 minutes). Upon completion of co-registration, the Artemis™ system will be used to target suspicious lesions identified by MP MRI and these biopsies and locations will be mapped within the Artemis software. A total of four computerized targeted biopsies per MP MRI lesion will be made using the Artemis™ system.

## **4. STUDY DESIGN**

Subjects are enrolled on the basis of elevated clinical suspicion for prostate cancer and identifiable area of suspicion on routine mpMRI. Subjects will initially be identified from the population of men undergoing outpatient management for suspected or known prostate cancer at NYU Smilow Prostate Cancer Center (SPCC) by members of the patient's treatment team or members of the investigational team. An investigator will screen the patients for eligibility in the study, and all information will be obtained either directly from the patient and/or their medical record. Initial screening will be based on suspicion for prostate cancer demonstrated by mpMRI of the prostate obtained as part of

the standard of care at NYU SPCC. Screening will be followed by evaluation of exclusion criteria for enrollment into the study.

### ***Inclusion Criteria***

1. Men 40-85 years of age
2. No contraindication to prostate biopsy (e.g. coagulopathy, medical condition prohibiting abstinence from anti-platelet or anticoagulation therapies, anatomical considerations)
3. Area of suspicion or known cancer focus on previously obtained mpMRI of the prostate (at least one lesion with MRI suspicion score > 2/5)

### ***Exclusion Criteria***

1. Prior pelvic radiotherapy
2. Evidence of urinary tract infection or significant urinary retention
3. Prostate instrumentation (e.g. prostate biopsy, transurethral prostate procedure) within 2 months prior to mpMRI
4. No evidence of suspicious lesions on mpMRI
5. Irreversible coagulopathy
6. Contraindication to sedation

#### **4.1 Study participation**

Subject participation includes one standard care biopsy session during which both transperineal and transrectal biopsies will be obtained using ultrasound/MRI fusion guidance to sample suspicious lesions identified on MRI. Two biopsy cores per lesion with MRI suspicion score > 2/5 will be obtained using each approach per standard practice. A follow-up visit after one week will be in accordance with current post-biopsy management practices, and further clinical management will proceed as per standard of care following the biopsy results.

Before enrollment, patients will undergo routine 3 Tesla mpMRI with T2 3D, DCE and DWI imaging following the NYULMC standard prostate imaging protocol. Each study will require approximately 45 minutes to acquire imaging. Prospective candidates for the study will undergo this imaging prior to enrollment into the study and biopsy. The results of the mpMRI will be provided according to the standardized NYULMC template. Lesions identified on mpMRI with high suspicion score (3, 4 or 5 out of 5) will be considered for targeting on biopsy. Men without evidence of lesion on mpMRI or with low suspicion lesions are not eligible for the study.

Study participants will then undergo standard of care pre-biopsy procedure including initiation of peri-procedure antibiotics and pre-procedure Fleets enema. Biopsy will be performed in the Smilow Prostate Cancer Center. All biopsies will be performed using general anesthesia per standard of care protocol. Biopsies will then be performed according to the standard procedure detailed below.

## 4.2 Intervention

Computerized targeting of mpMRI lesions will be performed using Artemis™ software system per standard practice. This software requires an initial transrectal ultrasound measurement of the prostate in order to obtain a 3D image of the prostate on ultrasound. The computerized co-registration will then be performed by software within the Artemis™ system and will fuse the MR imaging with real-time ultrasound imaging (this will require approximately 10 minutes). Upon completion of co-registration, the Artemis™ system will be used to target suspicious lesions identified by mpMRI and these biopsies and locations will be mapped within the Artemis software. A total of two computerized targeted biopsies per mpMRI lesion will be made using the Artemis™ system using each biopsy approach. A maximum of three mpMRI lesions will be targeted. The operator of the Artemis™ system biopsies will not be blinded to the mpMRI results. After completion of the targeted transrectal prostate biopsy, the patient will be repositioned to lithotomy position to expose the perineum. The physician will replace the transrectal ultrasound probe and obtain biopsies through transperineal needle placement into the same targets planned on the Artemis fusion software. Biopsy specimens will be collected in labeled jars for transport to the pathology lab in accordance with biopsies that are already performed as part of a patient's regular treatment at NYU Smilow Cancer Center. No additional cores will be collected for this study than what is normally taken for a standard of care whole biopsy (non-targeted and targeted biopsy). The targeted biopsies will require between 5-10 minutes of time per approach to acquire. After pathology analysis, leftover tissue remaining after analysis will be not be kept for further research analysis and will not be discarded. All biopsies will be archived as required by law.

This is an outpatient procedure. Patients will undergo a voiding trial prior to discharge. If they fail same day voiding trial, a Foley catheter will be placed with a second trial performed approximately one week after treatment per standard care.

The targeted biopsies will require 4 cores per lesion for each patient. A maximum of three mpMRI lesions will be allowed to be targeted. It is very rare (<5% of positive mpMRI) for there to be more than three lesions identified on mpMRI. The 4 cores taken per targeted lesion is the current standard at the Smilow Prostate Cancer Center. Typically, a biopsy will be done through one approach (transrectal or transperineal). For the purposes of this study, both approaches will be used per targeted lesion. However, only two cores will be taken for each approach which will not result in any extra cores taken for research purposes. As both approaches are considered routine, performance of both approaches during a biopsy sitting should not result in an increased likelihood of comorbidity and will not extend a subject's time under anesthesia by any significance.

Risks of performing the two targeted biopsy approaches in one setting are the same risks inherent to traditional systematic standard care prostate biopsy, including bleeding, infection, urinary retention, and voiding dysfunction.

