## 4.3 Endpoints

i. Predictor variables:

- a. Biopsy approach
  - i. *Variable type:* Dichotomous (categorical)
  - ii. *Potential outcomes:* Transperineal vs Transrectal
- b. Location of target lesion within the prostate is a prominent consideration for targeting accuracy, as lesions in the anterior prostate are known to be difficult to access using a posterior approach (transrectal biopsy).
  - i. *Variable type:* Categorical
  - ii. *Potential outcomes:* (Left vs right) + (Anterior vs posterior) + (apex vs midgland vs base)

ii. Outcome variables:

- a. Length of core-cancer involvement - A larger amount of cancer within each core as a result of improved lesion targeting provides better disease characterization. Data regarding core cancer length measurements in transperineal targeted biopsy is limited. Previous studies have shown median CCL in MRI-targeted transperineal biopsy to be 2mm (range 1-5mm). However, MRI-guided biopsies were performed under cognitive US-MRI fusion and thus did not benefit from automated image coregistration, which was shown to significantly increase mean CCL. To our knowledge there is no precedent for estimation of CCL in targeted transperineal biopsies using automated US/MRI fusion.
  - i. *Variable type:* Continuous
  - ii. *Scale:* millimeters
  - iii. *Validity:* Greater tumor length per core provides better diagnostic information and has been shown to correlate with Gleason score and pathologic stage at radical prostatectomy.
  - iv. *Source:* Histological analysis (pathologist's report)
- b. Number of cancers detected using each approach- The relative cancer detection rates (CDRs) between approaches correlate to the sensitivity of detecting cancer in high risk foci, and should be directly compared between the two modalities as a marker of targeting accuracy.
  - i. *Variable type:* Continuous
  - ii. *Potential outcomes:* 0-100%
  - iii. *Validity:* Since each lesion serves as its own control, a higher percentage of cancer-positive results using a given approach directly corresponds to accuracy of targeting using that technique
  - iv. *Source:* Histological analysis (pathologist's report)

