Positive results will be compared on a per-lesion basis, where the largest CCL of the two cores taken from each approach will be compared. Preliminary data from MRI-targeted biopsy since 2012 at the NYU SPCC has demonstrated approximately 55% and 95% cancer detection rate among patients with MRI suspicion scores of 4 and 5, respectively. Additionally, the average number of cancer-positive lesions among men with prostate cancer detected on targeted biopsy is 1.2. Given the approximate time-course for the study, accrual rate, cancer detection rate in our previous trial, and potential screen failures, we anticipate that recruitment of 80 patients will be feasible and provide sufficient power to demonstrate a difference of 1.0 mm in cancer-core length between the two techniques. This sample size also accounts for potential screen failure for patients consented who have not yet had their standard of care MRI of the prostate.

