### **Statistical analysis for primary objective**

Measurements of cancer-core length from transrectal and transperineal biopsies may be compared using a two-tailed, paired samples T test or Wilcoxon Signed Rank Test in order to accept or reject the hypothesis that transperineal biopsy provides higher CCL per positive core than transrectal biopsy.

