### **Statistical analysis for secondary objectives**

Cancer detection rate (CDR) and concordance may also be compared between techniques using McNemar's test. Multivariate analysis to determine predictors of improved diagnosis with either technique will be performed using binomial logistic regression.

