## 5.2 Diagnostic Intervention

B. Artemis Biopsy: Artemis, Eigen's 3-D prostate imaging device, is a FDA approved Class II medical device for planning and guiding a transrectal prostate biopsy.

In MRI/TRUS fusion planning, the previously available imaging study (MRI) is used by a trained radiologist to mark out regions of interest for targeting. This information is transferred to Artemis when a fusion plan is initiated. The MRI image and the 3D TRUS image are co-registered, and regions of interest marked on the MRI are mapped on to the 3D TRUS image. The urologist then plans biopsy targets in these regions of interest that are overlaid on the 3D TRUS image.

After planning, traditional needle guidance to the planned location as per normal biopsy technique is performed. At all times, the physician uses the live ultrasound image and Artemis guidance to biopsy tissue from the planned location. Transrectal Artemis biopsy is not investigational. This is currently the standard of care biopsy in our practice at NYU. It is FDA approved for this application, has several publications regarding technique from many institutions, and NYU urologic oncologists have performed roughly 1200 such biopsies at NYU since 2009, as part of our standard clinical protocol.

A new attachment will be added to the Artemis device to facilitate transperineal targeted biopsy. Transperineal biopsy itself is not investigational. This is a well-described biopsy technique that is used often in contemporary clinical practice, frequently to improve sampling when patients have a history of negative transrectal biopsies. The attachment to the Artemis device does have 510K regulatory clearance and we do not anticipate additional risks to standard of care transperineal biopsy.

After obtaining 2 cores of the suspicious lesion via transrectal Artemis biopsy, the patient is repositioned to allow for transperineal needle access. The Artemis fusion system allows for visualization of the previously accessed target and 2 additional cores are obtained via transperineal placement of the biopsy needle. For sequential patients, we will switch the order (transperineal before transrectal) for every other patient in order to mitigate any bias from starting with the same approach for each case.

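### Section 4.2 gives one biopsy order and omits the alternation in section 5.2, and order is not used in the predictors or the primary paired test

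*Combined protocol and SAP*

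**What the plan says.** Section 4.1 refers the reader to the procedure described after it. Section 4.2 (Intervention) then gives one sequence: "After completion of the targeted transrectal prostate biopsy, the patient will be repositioned to lithotomy position to expose the perineum". It mentions no other order and does not refer to section 5.2.

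Section 5.2 (Diagnostic Intervention) opens with the same sequence: "After obtaining 2 cores of the suspicious lesion via transrectal Artemis biopsy, the patient is repositioned to allow for transperineal needle access". Its last sentence then changes the rule: "For sequential patients, we will switch the order (transperineal before transrectal) for every other patient in order to mitigate any bias".

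Order does not appear again:

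- Section 4.3 lists two predictors, biopsy approach and lesion location. The second is justified on the ground that "Location of target lesion within the prostate is a prominent consideration for targeting accuracy".
- The primary analysis in section 4.5 is a "two-tailed, paired samples T test or Wilcoxon Signed Rank Test", with no order term.
- The secondary analyses are McNemar's test and a regression without listed covariates: "Multivariate analysis to determine predictors of improved diagnosis with either technique will be performed using binomial logistic regression".
- The unit of analysis is the lesion: "Positive results will be compared on a per-lesion basis, where the largest CCL of the two cores taken from each approach will be compared".

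**The concern.** There are two linked problems.

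First, the section that tells staff how to do the procedure leaves out the order rule that a later section adopts. Anyone working from section 4.2 alone would do transrectal first in every patient. Approach and order would then be the same variable. The second approach enters a target that has already been cored, after the patient has been repositioned, so an effect of order on core cancer length (CCL) is plausible. Under a fixed order, such an effect could create or hide the planned 1.0 mm difference.

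Second, section 5.2 treats order as a possible source of bias, but the analysis ignores it. Alternation balances patients, whereas the comparison is made on cancer-positive lesions, with up to three targets per man. Balance by order among analyzed lesions is therefore left to chance. No section says that the order used will be recorded or reported, so a reader could not confirm afterwards that the alternation took place.

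**Working it through.** **Inputs from section 4.5.** Mean difference 1.0 mm, SD 2.4 mm, alpha 5%, power 80%, 46 cancer-positive lesions, 80 patients, and an average of 1.2 positive lesions per man with cancer on targeted biopsy. The test is two-sided.

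**Assumption.** Let g be the CCL of the second approach minus that of the first. The documents give no value, so 0.25, 0.5 and 1.0 mm are used as a range. Differences are taken as normal and lesions as independent.

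**The plan's figure.** n = (2.4 × (1.960 + 0.842) / 1.0)² = 45.2, rounded up to 46. The plan's number is reproduced. The exact paired t power at 46 is 79.0%, which is the reference below.

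**Case A: section 4.2 followed literally (fixed order).** The paired test estimates δ + g, where δ is the true transperineal minus transrectal difference. Noncentral t, n = 46, SD 2.4:

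| Size of g (mm) | False positives, δ = 0 | Power, δ = 1.0, g a second-pass penalty |
|---|---|---|
| 0 | 5% | 79% |
| 0.25 | 10.6% | 55% |
| 0.5 | 28.2% | 28% |
| 1.0 | 79.0% | 5% |

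**Case B: section 5.2 followed (alternation).** The paired difference has mean δ + g in transrectal-first patients and δ − g in the others. Without an order term, two things follow:

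- The estimate is δ + g(n₁ − n₂)/n, where n₁ and n₂ are the analyzed lesions in each order. The bias is zero on average and depends on chance imbalance.
- The variance of the differences rises by about (2.4² + g²)/2.4² = 1.011, 1.043 or 1.174.

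Simulation with 80 patients split 40/40, 46 positive lesions at one per positive man, and 200,000 runs per setting:

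| g (mm) | Type I error, no term | Power, no term | Power, with term |
|---|---|---|---|
| 0.25 | 5.0% | 78.7% | 78.6% |
| 0.5 | 4.7% | 77.4% | 78.5% |
| 1.0 | 4.0% | 73.1% | 78.5% |

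If the number of positive lesions is random with 46 expected, the corresponding power is 76.3-77.0% without and 77.1-78.1% with the term at 0.5 mm. At 1.0 mm it is 71.8-73.7% without and 77.4-78.7% with.

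**Imbalance by order among analyzed lesions, |n₁ − n₂|/n.** With exactly 46 lesions at one per man, the mean is 7.6% and the 95th percentile 17.4%. With 1.2 lesions per positive man (80% with one, 20% with two), the mean is 10.3% and the 95th percentile 25.6%. The typical chance bias is therefore 0.076 to 0.103 times g: 0.04-0.05 mm for g = 0.5 and 0.08-0.10 mm for g = 1.0. The variance and imbalance figures describe the same omitted term and must not be added together.

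**A less favorable realized split, 28 against 18.** The bias is g × 10/46, which is 0.11 mm at 0.5 and 0.22 mm at 1.0. The unadjusted test then has type I error of 5.6-6.9%. Its power at δ = 1.0 is 68% (g = −0.5) or 52% (g = −1.0). With an order term, type I error is about 5% and power 77%. At one lesion per man, a split this uneven or worse arises in about 4% of trials.

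**The case against.** The strongest reply is that the documents largely settle the order themselves. Section 5.2 narrates the same base sequence as section 4.2 and then adds the alternation, and section 4.2 never says that its sequence applies to every patient. On that reading the gap is a missing cross-reference, and the Case A error rates belong to a trial nobody intends to run. This stands as far as it goes: the trial does not lack order control, and Case A is conditional.

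Under alternation, an unadjusted paired test is valid and the harm is small unless the order effect is as large as the whole planned difference. That also stands, and it is why the concern does not touch the validity of the design.

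A third point is that 2.4 mm may be read as the total SD of the paired differences, order variation included. The unadjusted test then keeps 79-80% power at all three order effects. However, section 4.5 takes 2.4 mm from pairs of transrectal cores in the same lesion, not from two approaches done in sequence, so adding order variation to it is reasonable. Even on the other reading the order term does not hurt, and at 1.0 mm it raises power from about 80% to 86%.

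Finally, the regression's silence on order is weak evidence, because it lists no covariates at all. Likewise, the absence of recording is inferred from silence. Both are fair. What remains is that a factor the design deliberately controls appears nowhere in the analysis.

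**Conclusion.** The concern holds and should be fixed. Sections 4.2 and 5.2 need to be reconciled, and the order of approaches should enter the primary comparison.

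The size depends on which section is followed. With the alternation, which is the natural reading, the loss is modest: at most about 1-2 points of power for a 0.5 mm order effect and about 5-6 points for 1.0 mm, plus a small chance bias that the plan would neither adjust for nor report. With section 4.2 taken literally, the comparison of approaches could not be interpreted if order has any material effect.

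The omission from the text is certain. The magnitudes rest on assumed order effects, normal differences and independent lesions. Nothing here makes 46 lesions wrong: with the order term and reasonable balance, power stays at about 79%, close to the planned value.

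**What to change.** 1. State the alternation of section 5.2 in section 4.2, so that one order rule governs.
2. Record the order actually used for each patient.
3. Include order in the primary paired comparison. For the t test, average the mean paired differences of the two order groups and use the pooled within-group variance. If the rank test is kept, the counterpart is a rank-sum test of the second-minus-first differences between the two order groups.
4. Report the number of analyzed lesions by order.

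Replacing alternation with a randomized list is optional, since every targeted lesion receives both approaches.

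The cost is one sentence in section 4.2, one data field, one model term (one degree of freedom) and one reported count. No extra core, procedure or patient is needed.

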#### **4.4 Follow-up**

The first clinical follow-up visit will be scheduled 1 week after biopsy. At that time the patient's clinical condition will be assessed according to standard of care post-biopsy evaluation. All study participants will be evaluated for additional complications to ensure that the targeted biopsies do not confer additional risk for complications. However, given that the maximum number of biopsies will be within the standard of care range, we do not anticipate an increase in complication rates. Biopsy results will be revealed to the patient at that time.

The primary endpoint of the trial will be assessed upon accrual and biopsy of the planned number of study participants. The primary objective will be assessed by quantifying the core cancer lengths of positive biopsy results (diagnosis of CaP, Gleason 3 or higher, in any given core) for each technique of targeted biopsy. Secondary endpoints will be evaluated via rate of positive biopsy using transperineal versus transrectal targeted techniques for prostate sampling. Furthermore, cancer characteristics including Gleason score and disease volume will be evaluated across techniques. All adverse event data will also be recorded.

Patients diagnosed with CaP will be offered standard of care treatment options as based upon the stage and grade characteristics of the identified disease. Targeted biopsy results that reveal CaP will be considered in the same fashion as CaP diagnosed with standard of care biopsy. All recommendations regarding the appropriate management of any CaP diagnosed will then be based upon biopsy features and patient decision.

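### The pathologist whose report supplies the primary endpoint is not masked to biopsy approach; approach-neutral core numbers would remove an avoidable risk of expectation bias

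*Combined protocol and SAP*

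**What the plan says.** - Section 1: "This is a prospective, open-label, single-center trial". Section 2.2 states a directional expectation, that "transperineal targeted biopsy will result in larger core-cancer length than transrectal biopsy".
- Section 4.3 gives the pathologist's report as the source for both CCL and cancer positivity. Section 4.4 adds that "cancer characteristics including Gleason score and disease volume will be evaluated across techniques".
- Section 4.2, on specimens: "Biopsy specimens will be collected in labeled jars for transport to the pathology lab in accordance with biopsies that are already performed" in regular care. What the label or the pathology request shows is not described.
- Section 4.2 also says that a biopsy normally uses one approach only, and that this study takes two cores by each approach from every targeted lesion. Section 4.5 compares the larger CCL of the two cores from each approach, lesion by lesion, so the study must know which core came from which approach.
- The only explicit statement on blinding in the protocol text is in section 4.2, and it concerns the biopsy operator, who "will not be blinded to the mpMRI results".
- Three other provisions might be taken for masking but are not. Section 5.2 alternates the order of the approaches between patients. Section 7.7 de-identifies study documents. Section 8 gives each patient a number.

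**The concern.** The reader of the cores generates the primary endpoint, and the plan leaves open whether that reader sees the approach. Routine labelling does not settle this. With one approach per biopsy, a routine label has no need to separate two approaches within a lesion. This study does have that need, and writing the approach on the jar or request is an obvious way to meet it.

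If the approach is visible, expectation could move readings in one direction. Pairing within a lesion cancels what the two approaches share, namely the patient, the lesion and the habits of the reader. It does not cancel a shift tied to the approach, which passes straight into the paired difference. Taking the larger of two cores does not remove a shift that affects both. Alternating the biopsy order deals with order effects and not with the reading step.

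Cancer positivity and biopsy Gleason score are read by the same route, so the secondary comparisons are exposed in the same way.

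**Working it through.** **Inputs.** From section 4.5: 46 cancer-positive lesions, mean difference 1.0 mm, SD 2.4 mm, α 5%, power 80%, and a two-tailed paired t test or Wilcoxon signed-rank test. The reading shift *b* is an assumption; the documents give no value for it.

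**1. The plan's own figure.** Paired normal approximation:

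n = ((1.960 + 0.842) × 2.4 / 1.0)² = 45.2, rounded up to 46.

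The stated 46 reproduces. The exact paired t test gives 79.0% power at 46 lesions, so the plan's figure is accepted here.

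**2. Significance threshold.** Standard error = 2.4 / √46 = 0.354 mm. With t(0.975, 45 df) = 2.014, the smallest observed mean difference that reaches significance is 2.014 × 0.354 = 0.71 mm, against a design effect of 1.0 mm.

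**3. Effect of a reading shift when there is no true difference.** A mean shift *b* gives a noncentral t statistic with 45 df and noncentrality *b* / 0.354. The false-positive rate is the probability that its absolute value exceeds 2.014. The Wilcoxon column comes from 40,000 simulated trials per row.

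| Mean shift (mm) | Noncentrality | Paired t | Wilcoxon |
|---|---|---|---|
| 0 | 0 | 5.0% | 5.0% |
| 0.1 | 0.28 | 5.9% | 6.0% |
| 0.25 | 0.71 | 10.6% | 10.5% |
| 0.5 | 1.41 | 28.2% | 27.2% |

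A shift of about 0.24 mm doubles the nominal 5%.

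**4. The same shifts in concrete terms.** Suppose one approach is read 1 mm longer in *k* of the 46 lesions, a mean shift of *k*/46 mm. By simulation (t test):

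- *k* = 5 (0.11 mm): about 6%
- *k* = 12 (0.26 mm): about 10%
- *k* = 23 (0.50 mm): about 27%

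**5. Sensitivity to the SD.** In section 4.5 the 2.4 mm belongs to the difference between the largest and second-largest CCL of a lesion (2.1 ± 2.4 mm), which cannot be negative. If that difference is given a random sign, the SD becomes √(2.1² + 2.4²) = √10.17 = 3.19 mm. The standard error is then 0.470 mm, the threshold is 2.014 × 0.470 = 0.95 mm, and the three false-positive rates are 5.5%, 8.2% and 18.0%.

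**The case against.** The harm needs three things that the documents do not establish: the label or request shows the approach, the reader knows or shares the hypothesis, and this moves a measurement in millimetres. Specimens go to the institution's pathology laboratory under routine handling, and no available text makes the pathologist an investigator. Open-label status alone does not show that the reader is unmasked. This is right, and it is why the point is an avoidable risk and not a demonstrated bias.

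The upper end of the range is strained. A 0.5 mm mean shift means reading 1 mm too long in half the lesions, always for the same approach. Where the favoured approach's cores hold no cancer there is no length to over-read, so the shift would have to come from fewer lesions. With the larger SD the rates fall. These points stand and argue for weight on the low to middle part of the range. They reduce the effect without removing it.

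The remedy also has costs:

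- The laboratory must accept a study-specific label.
- No section places study staff in the procedure room.
- The Artemis map is not said to record approach or jar number.
- A swapped link would reverse the sign of that lesion's paired difference.
- Tissue in the core might reveal the route (an assumption; the documents do not address it).
- Section 3.1 links transperineal findings to focal-therapy planning, so the approach may matter clinically.

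The last point has an answer: section 6.1 says participants are under the investigators' care, so the link record keeps the approach available to them. The others must be managed, but none outweighs protection of the primary endpoint.

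**Conclusion.** The concern holds. The primary endpoint and the two secondary pathology measures rest on a reading step for which the plan states no masking to approach, in an open-label trial with a directional hypothesis. The plan's other bias controls do not reach that step.

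The size of any bias is unknown. Across assumed mean shifts of 0.1 to 0.5 mm, the false-positive rate of the paired t test would be 5.9% to 28.2% at the plan's SD, or 5.5% to 18.0% at an SD of 3.19 mm. At the low end the effect is close to nil. These figures assume 46 analysed lesions, no true difference and approximately normal paired differences.

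The change is recommended rather than essential. It is worth making before the first biopsy, because masking cannot be restored once reports have been issued. If approach-neutral labelling is already the practice, saying so is enough.

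**What to change.** **Section 4.2.** Label targeted-core jars and the pathology request with patient, lesion, site and a core number that does not reveal the approach. Assign the numbers in random order within each patient. Avoid a fixed approach order or order of collection, since sections 4.2 and 5.2 make either one guessable. Name the person who records the link between core number and approach at the time of biopsy, alongside the fusion record, where "these biopsies and locations will be mapped within the Artemis software". Have that person confirm each entry before the jar leaves the room. Keep the link available to the treating investigators but out of the pathology request.

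**Section 4.3.** State that CCL, cancer positivity and biopsy Gleason score are reported without knowledge of approach, and that approach is joined to the study data only after the report is final.

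**Section 8.** Add the specimen-level code; the present text codes patients only.

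**Cost.** One number list and one link record per patient, for at most 3 lesions × 4 cores = 12 targeted cores, plus the laboratory's agreement to the label. There is no extra core, patient, reader or repeat reading, no delay to the clinical report, and no change to the 46 lesions. The remaining downsides are a possible linking error and masking that may be incomplete.
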